9.1.1. Premedication

Infusion-related reactions, including Grade 3-5 IRR events, have been observed with olatumab. To date, Grade 3-5 IRR events have primarily occurred during the first cycle of olatumab treatment. Therefore, premedicate all patients with the following (or equivalent) medications: a histamine H1 antagonist (eg, diphenhydramine) and dexamethasone intravenously 30–60 minutes prior to the olatumab/placebo doses on Days 1 and 8 of Cycle 1.

For subsequent cycles, premedicate all patients with a histamine H1 antagonist (eg, diphenhydramine) intravenously 30-60 minutes prior to each dose of olatumab/placebo.

Premedication with additional agents may be provided at investigator discretion.

Premedication **must be** provided in the setting of a prior Grade 1 or 2 olatumab/placebo IRR, as detailed in Section 9.4.1.1.1.1. All premedication administered must be adequately documented in the eCRF.

Given the emetogenic potential of doxorubicin, premedication with antiemetics per institutional guidelines is recommended. Additional premedication may be provided at investigator discretion.

If doxorubicin premedication is required prior to the doxorubicin infusion, this must be done after the completion of olatumab/placebo infusion, not before the olatumab/placebo infusion. This premedication may be administered immediately following the end of the observation period (if applicable) or after the completion of the olatumab/placebo infusion.

Starting with Cycle 1, dexrazoxane may be administered IV at a 10:1 ratio (dexrazoxane:doxorubicin) at the investigator's discretion, according to instructions provided in the Pharmacy Manual for this study, beginning no later than 30 minutes prior to each doxorubicin infusion for the prevention of cardiotoxicity. It is recommended that all patients receiving 5 or more cycles of doxorubicin receive dexrazoxane.

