Patients will receive combination treatment for 8 cycles followed by monotherapy olaratumab or placebo until evidence of progressive disease (PD), unacceptable toxicity, death, or other withdrawal criteria are met. No crossover will be permitted.

Diagnosis and Main Criteria for Inclusion and Exclusions: Patients at least 18 years of age, ECOG PS 0 to 1, anthracycline naïve, with histologically confirmed, advanced or metastatic STS, and not amenable to treatment with surgical resection or radiotherapy with curative intent. Patients with gastrointestinal stromal tumor (GIST) or Kaposi's sarcoma will be excluded.

Test Product, Dosage, and Mode of Administration: Olaratumab: injection for intravenous (IV) use, supplied in single-use 500 mg/50 mL vials containing 10 mg/mL of product in histidine buffer, administered to patients as an IV infusion at a loading dose of 20 mg/kg on Days 1 and 8 in Cycle 1, followed by 15 mg/kg on Days 1 and 8 in subsequent cycles. Cycles are 21 days in length.

Reference Therapy, Dose, and Mode of Administration: Placebo: injection for IV use, supplied in single-use vials, administered to patients as an IV infusion on Days 1 and 8. Doxorubicin: commercial formulations will be used and administered intravenously. Doxorubicin (75 mg/m²) is to be administered on Day 1 of each 21-day cycle, for 8 cycles. Dexrazoxane: Commercially available dexrazoxane may be administered starting at Cycle 1 at a 10:1 ratio (dexrazoxane:doxorubicin) at the investigator's discretion, prior to the doxorubicin infusion for the prevention of cardiotoxicity and its use is recommended in patients receiving 5 or more cycles of doxorubicin. Dexrazoxane should be administered after completion of the olaratumab/placebo infusion, prior to administration of doxorubicin. Doxorubicin should be administered within 30 minutes of receiving dexrazoxane.

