- Doxorubicin (after the olaratumab administration and 1-hour observation period, if instituted) on Day 1 of every 3-week cycle administered according to institutional guidelines and/or clinical practice, as an IV injection or as an infusion to be administered in less than 60 minutes for 8 cycles. Starting with Cycle 1, dexrazoxane may be administered at a 10:1 ratio (dexrazoxane:doxorubicin) at the investigator's discretion according to instructions provided in the Pharmacy Manual for this study, beginning within 30 minutes prior to each doxorubicin infusion for the prevention of cardiotoxicity. It is recommended that all patients receiving 5 or more cycles of doxorubicin receive dexrazoxane.

Patients in the control **Arm B** will receive:

- Placebo on Day 1 and Day 8 of every 3-week cycle as an IV infusion over approximately 60 minutes, followed by a 1-hour observation period for the first 2 cycles. If there is no evidence of an IRR after the D1 and D8 infusions of placebo during the first 2 cycles, no observation period is required for subsequent treatment cycles. In the event that a Grade 1 or 2 IRR occurs after Cycle 2, the 1-hour observation period will be reinstated for a minimum of 2 cycles. The reinstated observation period may be suspended after 2 cycles if the patient shows no further signs or symptoms of an IRR.
- Doxorubicin (after the placebo administration and 1-hour observation period, if instituted) on Day 1 of every 3-week cycle administered according to institutional guidelines and/or clinical practice, as an IV injection or as an infusion to be administered in less than 60 minutes for 8 cycles. Starting with Cycle 1, dexrazoxane may be administered IV at a 10:1 ratio (dexrazoxane:doxorubicin) at the investigator's discretion according to instructions provided in the Pharmacy Manual for this study, beginning within 30 minutes prior to each doxorubicin infusion for the prevention of cardiotoxicity. It is recommended that all patients receiving 5 or more cycles of doxorubicin receive dexrazoxane.

Administration and dosing of all therapeutic products will occur as described in Section 9.1.

Criteria for starting the next cycle are defined in Section 9.4.1.1. Dose reductions for olaratumab/placebo will be made in the event of specific treatment-related AEs, as described in Section 9.4.1.1.1. Supportive care guidelines are detailed in Section 9.6.1. No dose escalations or re-escalations are permitted.

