- ^b A 1-hour (+5 minutes) Observation Period is required after the administration of the initial 2 cycles of olaratumab/placebo. During the Observation Period, collect vital signs 3 times: 1) within 15 minutes (+5 minutes) prior to olaratumab/placebo infusion, 2) within 1 hour (+5 minutes) after completion of the olaratumab/placebo infusion, and 3) within 1 hour (+5 minutes) after completion of the doxorubicin infusion. If there is no evidence of an IRR during the initial 2 cycles of olaratumab/placebo, then no observation period is required for subsequent treatment cycles. In the event an IRR occurs thereafter, then the 1-hour observation period should be reinstated, see Section 9.2.1. Thereafter (Cycles 3+), obtain vital signs 2 times: 1) within 15 minutes (+5 minutes) prior to olaratumab/placebo infusion and 2) within 1 hour (+5 minutes) after completion of the doxorubicin infusion.
- ^c Administer doxorubicin according to institutional guidelines and/or clinical practice as an IV injection or as an infusion in less than 60 minutes. Decrease the rate of doxorubicin administration if erythematous streaking along the vein proximal to the site of infusion or facial flushing occur. Infusion or injection start and end times will need to be recorded. Starting with Cycle 1, dexrazoxane may be administered at a 10:1 ratio (dexrazoxane:doxorubicin) at the investigator's discretion according to instructions provided in the Pharmacy Manual for this study, beginning within 30 minutes prior to the doxorubicin infusion for prevention of cardiotoxicity. It is recommended that all patients receiving 5 or more cycles of doxorubicin receive dexrazoxane.

Any measurements used to determine dose should be taken at each cycle, and dose should be recalculated for each cycle.

The investigator or his/her designee is responsible for the following:

- explaining the correct use of the drugs and planned duration of each individual's treatment to the patient/site personnel/legal representative,
- verifying that instructions are followed properly,
- maintaining accurate records of study drug dispensing and collection,
- and returning all unused medication to Lilly or its designee at the end of the study.

Note: In some cases, sites may destroy the material if, during the investigator site selection, the evaluator has verified and documented that the site has appropriate facilities and written procedures to dispose clinical trial materials.

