9.2.2. Doxorubicin

Investigators should consult the approved doxorubicin hydrochloride package insert for complete prescribing information (including warnings, precautions, contraindications, adverse reactions, and dose modifications) and follow institutional procedures for the administration of doxorubicin. If a patient should have an IRR to doxorubicin, the investigator should follow the manufacturer's recommendations and clinical guidelines in the management of the patient.

Doxorubicin 75 mg/m² is administered IV. The dose of doxorubicin should be reconstituted in 100 mL of normal saline. Administer doxorubicin as an IV injection or as an infusion in less than 60 minutes. Decrease the rate of doxorubicin administration if erythematous streaking along the vein proximal to the site of infusion or facial flushing occur.

Doxorubicin must be reconstituted prior to infusion. The reconstituted solution is stable for 7 days at room temperature and under normal room light and 15 days under refrigeration (2°C to 8°C). It should be protected from exposure to sunlight.

Parenteral drug products should be inspected visually for particulate matter and discoloration prior to administration, whenever solution and container permit.

See Section 9.6.1.1 for dexrazoxane administration. Dexrazoxane should be started within 30 minutes prior to the doxorubicin infusion.

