9.6.1.1. Dexrazoxane

Starting with Cycle 1, dexrazoxane may be administered IV at the investigator's discretion according to instructions provided in the Pharmacy Manual for this study, beginning within 30 minutes prior to each doxorubicin infusion for the prevention of cardiotoxicity. It is recommended that all patients receiving 5 or more cycles of doxorubicin receive dexrazoxane. Investigators should consult the dexrazoxane information provided in the Pharmacy Manual for

this study for administration information (including warnings, precautions, contraindications, adverse reactions, and dose modifications).

Note that as the dose of dexrazoxane administered is dependent on the dose of doxorubicin administered, any dose modifications to doxorubicin will require a corresponding dose modification to dexrazoxane in order to maintain a dosage ratio of 10:1 (dexrazoxane:doxorubicin).

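### Protocol 9.1.1 makes 30 minutes the minimum lead time for starting dexrazoxane before doxorubicin; four other protocol sections make it the maximum, so the two rules share no practical window.

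*Protocol*

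**What the plan says.** Dexrazoxane is optional. Section 9.6.1.1 opens with "Starting with Cycle 1, dexrazoxane may be administered IV" and leaves the decision to the investigator. The protocol recommends it for patients who receive five or more cycles of doxorubicin; eight cycles are planned.

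The timing of the start is given in five places:

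- Section 9.1.1 (Premedication): "beginning no later than 30 minutes prior to each doxorubicin infusion".
- Section 8.1.1, once for each arm: "beginning within 30 minutes prior to each doxorubicin infusion for the prevention of cardiotoxicity".
- Table JGDJ.1, footnote c, in Section 9.1: "beginning within 30 minutes prior to the doxorubicin infusion for prevention of cardiotoxicity".
- Section 9.2.2 (Doxorubicin): "Dexrazoxane should be started within 30 minutes prior to the doxorubicin infusion".
- Section 9.6.1.1 (Dexrazoxane): the same timing phrase as Section 8.1.1.

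The synopsis has a sixth statement, framed from the doxorubicin side: "Doxorubicin should be administered within 30 minutes of receiving dexrazoxane".

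In the treatment-period table of the Study Schedule (Attachment 1), the dexrazoxane row cites Section 9.1.1 and the doxorubicin row cites Section 9.2.2. Section 9.2.2 in turn refers to Section 9.6.1.1 for dexrazoxane. Sections 8.1.1, 9.1.1 and 9.6.1.1 and footnote c also refer to a Pharmacy Manual, which is not among the documents.

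**The concern.** The wording of Section 9.1.1 and that of the other four sections look alike but run in opposite directions. A start no later than 30 minutes before doxorubicin sets a floor on the lead time. A start within the 30 minutes before doxorubicin sets a ceiling. All of this is current protocol text, not the amendment summary.

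What is at stake is conduct and monitoring. Site staff have two instructions for one procedure, and a monitor has no single standard for judging a timing deviation. It deserves attention because dexrazoxane is given to prevent cardiotoxicity, Section 9.4.1.1.2.2 says that cardiac risk rises with cumulative doxorubicin, and cardiac dysfunction is an adverse event of special interest (Sections 10.3.1.3 and 10.3.3.1).

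**Working it through.** The plan gives no figure to reproduce, and no sample size, event count or alpha enters. The check sets the statements side by side and intersects the windows that they define.

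Let S be the minutes from the start of dexrazoxane to the start of doxorubicin.

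| Place in the protocol | Reference point | Window for S |
|---|---|---|
| Section 9.1.1 | start of dexrazoxane | S ≥ 30 |
| Section 8.1.1, both arms | start of dexrazoxane | 0 ≤ S ≤ 30 |
| Table JGDJ.1, footnote c | start of dexrazoxane | 0 ≤ S ≤ 30 |
| Section 9.2.2 | start of dexrazoxane | 0 ≤ S ≤ 30 |
| Section 9.6.1.1 | start of dexrazoxane | 0 ≤ S ≤ 30 |
| Synopsis | receipt of dexrazoxane, start or end not stated | see below |

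**Section 9.1.1 against the other four.** The intersection of S ≥ 30 with 0 ≤ S ≤ 30 is the single value S = 30, an interval of width 30 − 30 = 0 minutes. Two examples:

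- S = 15 meets the four sections and breaks Section 9.1.1.
- S = 45 meets Section 9.1.1 and breaks the four sections.

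All five statements refer to when dexrazoxane begins, so a difference of reference point cannot explain the conflict.

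**The synopsis.** Two readings are open.

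- If receipt means the start, the synopsis gives 0 ≤ S ≤ 30. It then agrees with the four sections and conflicts with Section 9.1.1 in the same way.
- If receipt means the end, let D be the length of the dexrazoxane infusion and G the gap from its end to doxorubicin, with 0 ≤ G ≤ 30. Then S = D + G, so D ≤ S ≤ D + 30. The overlap with Section 9.1.1 runs from the larger of 30 and D up to D + 30, which has positive width for any D above 0. The overlap with the four sections runs from D to 30, which has positive width only if D is below 30.

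The documents do not give D. With D = 15, purely as an illustration, the synopsis would allow S from 15 to 45: the part from 30 to 45 meets Section 9.1.1 and the part from 15 to 30 meets the four sections. The synopsis is therefore ambiguous and cannot be counted for either side.

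**Result.** Section 9.1.1 stands against four sections, and the synopsis is unresolved.

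**The case against.** The strongest reply is that sites work from the Pharmacy Manual. Four of the five start-time statements point to it, and Section 9.6.1.1 sends investigators there for administration details. If the manual states one timing, practice may be uniform and Section 9.1.1 a slip of wording, perhaps meant as not more than 30 minutes before. This stands in part: the documents do not show that timing differs between sites. It does not remove the point. The manual cannot be inspected here, the protocol itself prescribes two timings, and the Study Schedule leads to both.

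Other objections limit what may be claimed, and they stand. A reader might infer any of the following, and the documents support none of them:

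- *That compliance with both rules is impossible.* A start at exactly 30 minutes satisfies both. What is missing is a practical common window.
- *That five other places contradict Section 9.1.1.* Four sections do; the synopsis is ambiguous.
- *That patients are less safe.* Nothing in the documents links lead time to cardioprotection or toxicity. Cardiac risk is also handled by ECG, by ECHO or MUGA, and by LVEF criteria for stopping doxorubicin.
- *That a planned analysis is compromised.* SAP 5.9 says only that an exploratory look at dexrazoxane use and cardiac dysfunction will be considered. The dexrazoxane exposure variables in SAP 5.14.1 cover duration, dose and dose intensity, not lead time.
- *That the arms are treated differently.* Section 8.1.1 gives the same dexrazoxane timing for each arm, under blinding.
- *That Section 9.1.1 is the text in error.* Being outnumbered does not show which timing was intended.

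**Conclusion.** The inconsistency is real and lies in current, operative text. Section 9.1.1 sets a lead time of 30 minutes or more; Sections 8.1.1, 9.2.2 and 9.6.1.1 and footnote c of Table JGDJ.1 set 30 minutes or less. The common window has zero width. This rests only on the plain meaning of the two phrases and on all five counting from the start of dexrazoxane.

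Its reach is limited to conduct and deviation monitoring for an optional agent. Dexrazoxane timing enters no calculation of overall survival, alpha or power, and any safety effect is unquantified. The point is worth correcting because the instruction is one that sites are sent to and correction is cheap. It is not evidence against the trial's efficacy conclusions.

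**What to change.** Reconcile Sections 9.1.1, 8.1.1 (both arm descriptions), 9.2.2 and 9.6.1.1, footnote c of Table JGDJ.1, the synopsis and the Pharmacy Manual so that one timing applies. State whether the interval counts from the start or the end of dexrazoxane. Giving the rule once, for instance in the dexrazoxane section, and cross-referring to it elsewhere would prevent the texts from drifting apart again. Point the dexrazoxane row of the Study Schedule to that section.

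Which timing is right is a clinical decision for the sponsor; this review does not make it. The number of phrases to edit depends on that decision, but in any case the work is wording changes in a few places, a check of the Pharmacy Manual, and a note to sites and monitors. No new data, sample-size change or SAP change is needed.

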9.2. Materials and Supplies

Olatumab and placebo will be provided to the sites by Lilly.

Study drug will be supplied as a sterile preservative-free solution for IV infusion in single-use vials containing 500 mg/50 mL of olaratumab (10 mg/mL) or placebo.

Olaratumab/placebo is formulated in 10 mM histidine, 100 mM glycine, 50 mM sodium chloride, 75 mM mannitol, and 0.02% polysorbate-20, pH 5.5. All excipients used in the formulation of olaratumab/placebo drug product are of pharmacopeia grade.

Where commercially available, doxorubicin hydrochloride will be purchased by the sites. In the event that there are regional restrictions or supply limitations, doxorubicin may be provided to the sites by Lilly.

Where commercially available, dexrazoxane will be purchased by the sites. In the event that there are regional restrictions or supply limitations, dexrazoxane may be provided to the sites by Lilly.

Clinical study materials will be labeled according to the country's regulatory requirements.

9.2.1. Olaratumab/Placebo

Olaratumab/Placebo Drug Product: The drug product must be stored under refrigeration at 2°C to 8°C (36°F-46°F) with protection from direct light. Do not freeze and/or shake olaratumab/placebo drug product. Stability studies have demonstrated that the drug product can withstand transient excursion to room temperature without adverse effect; however, storage at this temperature is not recommended.

Please refer to the pharmacy manual for olaratumab/placebo dosing solution for infusion.

CAUTION: Infusion-related reactions may occur during or following olaratumab/placebo administration (see Section 9.4.1.1.1 for a definition of Grade 3 and 4 IRRs). During the administration of olaratumab/placebo, patients should be in an area with resuscitation equipment and treatments necessary for advanced life support and cardiopulmonary resuscitation (CPR), such as bronchodilators, vasopressor agents (e.g., epinephrine), oxygen, glucocorticoids, antihistamines, IV fluids, and so forth. A 1-hour observation period is required after the administration of the first and second cycles of olaratumab/placebo. If there is no evidence of an IRR during the initial 2 cycles of olaratumab/placebo, then no observation period is required for subsequent treatment cycles. In the event that a Grade 1 or 2 IRR occurs after Cycle 2, the 1-hour observation period will be reinstated for a minimum of 2 cycles. The reinstated observation period may be suspended after 2 cycles if the patient shows no further signs or symptoms of an IRR.

9.2.2. Doxorubicin

Investigators should consult the approved doxorubicin hydrochloride package insert for complete prescribing information (including warnings, precautions, contraindications, adverse reactions, and dose modifications) and follow institutional procedures for the administration of doxorubicin. If a patient should have an IRR to doxorubicin, the investigator should follow the manufacturer's recommendations and clinical guidelines in the management of the patient.

Doxorubicin 75 mg/m² is administered IV. The dose of doxorubicin should be reconstituted in 100 mL of normal saline. Administer doxorubicin as an IV injection or as an infusion in less than 60 minutes. Decrease the rate of doxorubicin administration if erythematous streaking along the vein proximal to the site of infusion or facial flushing occur.

Doxorubicin must be reconstituted prior to infusion. The reconstituted solution is stable for 7 days at room temperature and under normal room light and 15 days under refrigeration (2°C to 8°C). It should be protected from exposure to sunlight.

Parenteral drug products should be inspected visually for particulate matter and discoloration prior to administration, whenever solution and container permit.

See Section 9.6.1.1 for dexrazoxane administration. Dexrazoxane should be started within 30 minutes prior to the doxorubicin infusion.

9.3. Method of Assignment to Treatment

Upon completion of all screening evaluations to confirm a patient's eligibility, the site will register the patient by the Interactive Web Response System (IWRS), which is web-based and accessible 24 hours a day. The IWRS registration consists of assigning the patient a unique study identification number for all patients randomized into 1 of the 2 treatment arms on a 1:1 basis.

The IWRS will assign patients to treatment arms according to a stratified method of randomization (that is, independent randomization within each of 48 strata or cells), defined by the following 4 prognostic factors:

- Number of prior systemic therapies for advanced/metastatic disease (0 versus ≥ 1)
NOTE: Any therapy administered in the adjuvant/neoadjuvant setting will not be considered as a prior line of therapy here.
- Histological tumor type (leiomyosarcoma versus liposarcoma versus undifferentiated pleomorphic sarcoma versus other STS types)
- ECOG performance status (0 versus 1)
- Region (North America versus Europe versus ROW)

Once the patient is registered through the IWRS, he/she is considered to be enrolled in the study. After randomization, patients should receive their first dose of treatment within 72 hours (3 days) whenever possible (up to 3 additional days delay of first dose of treatment will be permitted due to holidays, weekends, bad weather, or other unforeseen circumstances and will not count as a protocol deviation).

